This protocol is intended for a multicenter open label experimental, randomized controlled trial on the efficacy and safety of using first line AEDs as substitution therapy in childhood drug-resistant epilepsy. It will prospectively follow 100 children up during 14 weeks that consist of baseline, intervention, and post-intervention phases. While the intervention consists of 6 steps, as described at the Figure 1 below.

[figure not shown]

Figure 1. Timeline of the intervention phases

The study will be conducted at pediatric outpatient clinic of 3 referral hospitals in Jakarta, Cipto Mangunkusumo Hospital, Harapan Kita Hospital and Fatmawati Hospital. Children who are diagnosed with drug-resistant epilepsy receiving levetiracetam or topiramate will be enrolled in the study. Enrollment begins as soon as the research ethics committee approval is obtained from The Ethics Committee of The Faculty of Medicine, University of Indonesia-Cipto Mangunkusumo Hospital. The study will be closed after the last recruited patient has been followed up for the required 14 weeks.

All recruited children will be examined for monitoring at the hospital where the intervention is initiated. To avoid selection bias, all patients who met the inclusion criteria are divided into two groups, the intervention and control groups. Prospective participants and their parents will be provided with information related to the study. Patients will then fill out an information sheet containing demographic data, comorbidities, developmental history, school history, history of drug consumption, as well as history of seizures and patient complaints. All the data will be extracted and recorded on the case report form. Patients and their parents should be informed that participation is voluntary and they are free to withdraw from the study at any time. They should also be informed that refusal to participate or withdraw from the study will not affect the quality of treatment received. In the event of their withdrawal, it will be explained that the data collected so far is irrevocable, and we will seek consent to use such data in the final analysis if necessary.

Study procedure

Study procedures are depicted in Figure 2. The patients who are eligible for the study and have given their consents, will be enrolled, divided into 2 groups, the intervention and control, then start the 3-day baseline phase. In this phase, data such as demographic, clinical characteristic

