- 2. Children diagnosed as drug-resistant epilepsy by pediatric neurologists, diagnosis was based on the ILAE 2017 criteria
- 3. Children will have got at least 3 months of combination therapy that consists of levetiracetam of topiramate with optimal of therapeutic dosages

Exclusion criteria

- 1. Non-convulsive epilepsy
- 2. Suffered from status epilepticus in the prior 3 months before the study begins
- 3. Past medical history of idiosyncrasies or severe adverse drug reactions caused by the substitution therapy that will be given

Instrument of the study

QOLCE-55 questionnaire

Once the children are enrolled, quality of life will be assessed by using validated QOLCE-55 questionnaire. It is parent-reported and self-administered questionnaire which assess quality of life children with epilepsy age 4-18 years of age. The researcher will give a detail explanation about filling the questionnaire. It has 55 questions including cognitive (22 items), emotional (17 items), social (7 items) and also physical (9 items) function. Items are rated on a five-point Likert scale, 0 = very often, 1 = fairly often, 2 = sometime, 3 = almost never, 5 = never. The composite score is the unweighted average of the four subscales, ranging from 1-100, higher score indicates better quality of life.²⁸

Diary Card

The other important thing to evaluate is subjects' adherence, seizure frequencies, and adverse drug reaction by self-reported diary card which is filled by the parents each day during the intervention phase. Besides, drug consumption compliance is also assessed by counting the tablets or powder packages during routine visits of the study.

Electronic Medical Record

Electronic Medical Record is used to collect secondary data that include demographic data, clinical characteristic, and imaging such as brain-CT or brain-MRI.

Laboratory Examination

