The test is performed in hospitals' laboratory where the study take place and is done twice, at the baseline and post intervention phase. The order of the blood test consists of complete blood test, liver function test including alanine and aspartate transaminase, kidney function test including urea and creatinine, and also blood electrolyte that consist of natrium, kalium and calcium. The laboratory professional takes the blood from vein of the arm. The subjects are seated or lying down, accompanied by the parents, while for the younger children, they seat on his/her parents' lap or position that make them feel comfortable. Older children may be asked to make a fist and then will be tied by a rubber band around his/her arms. After that, the needle is inserted the needle until the blood is drawn. The laboratory worker will take the needle since the amount of blood is enough and puts an adhesive bandage over the site. The next step is analyzes of the sample and the result will be issued for about 1-2 days both printed or provided on the electronic medical record.

Electroencephalography Examination

The EEG examination is operated two times, at the baseline and post intervention phase, with high density machine (Caldwell Easy III) is done twice, pre- and post-intervention. The machine will operate for about 45 minutes including 5 minutes each for eye-open and eye-close in every subjects. Beginning with acquisition, EEG recordings use standard parameter to analyze brain activity at various frequencies to gain good quality and artefact-free result. The printed results of the EEG is available for about 4-7 days after the examination.

Data collection

All relevant data will be recorded, by nominated member(s) of the research team, on a case report form (CRF). Each participant will have a CRF and be assigned a unique identification number.

Baseline data

At entry into the study, the following baseline information will be recorded in the CRF:

- unique patient identification number contact telephone number and/or email address
- date of entry into the study
- eligibility for study entry based on inclusion/exclusion criteria
- age at study entry, in years and months
- gender
- weight and height
- seizure type (eg, generalized tonic clonic, absence, myoclonic and partial)
- the age at diagnosis and duration of epilepsy
- seizure frequency or average number of seizures per month

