- current anticonvulsant(s) with doses and formulation and its side effect (if presents)
- other medications and its side effect (if presents)

- first recognized seizure date
- prior EEG and laboratory which has been performed at the baseline phase
- physical examination

Follow-up data

Follow-up data will be collected during regularly scheduled clinic visits (per 2 weeks). This information will be obtained from the participants' diary card. Important information to be collected at follow-up will include:

- physical examination
- adverse drug reaction of the substitution therapy that happen
- seizure's frequency
- type of seizure
- complaint

Outcome evaluation

- a. The difference in responders was the difference in the percentage of responders in the group that used first line OAE again as substitution therapy and those that used standard therapy. Responders are subjects who experience a decrease frequency of seizure more than or equal to 50% of the initial seizure. Frequency of seizure is the number of seizures that occur within 1 month. In previous studies, it was said that the frequency of seizures was said to have decreased significantly or was said to respond if the seizures were reduced by 50% or more from the initial seizure. ^{19, 29} Based on this, researchers will categorize the frequency of seizures into:
 - Responder: there is a decrease in the frequency of seizures by 50% or more than before
 - Non-responder: namely the frequency of seizures remains or decreases but not up to 50% of the initial seizure frequency or the frequency is more than before

Furthermore, the proportion in the form of the percentage of respondents in the two groups is calculated and differentiated, therefore it is classified into two groups:

- Different : when a significant difference is shown in difference of proportion test of the 2 unpaired groups.
- Not different: when there is no significant difference is shown in difference of proportion test of the 2 unpaired groups.

- b. Differences in quality of life: quality of life assessment using QOLCE-55 instrument. The average of each function (cognitive, emotional, social and physical functions) and the average of the total functions are assessed. This variable is categorized into:
 - Different, if there is a difference in the average quality of life
 - Not different, if there is no difference in the average quality of life
- c. Differences in electroencephalography appearance

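### The primary endpoint is a percentage fall in a one-month seizure count, but no minimum baseline count or look-back is set, so response is unattainable at zero and largely chance at low counts

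*Combined protocol and SAP*

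**What the plan says.** The primary endpoint is a relative change. Outcome evaluation, item a, states: "Responders are subjects who experience a decrease frequency of seizure more than or equal to 50% of the initial seizure", and "Frequency of seizure is the number of seizures that occur within 1 month". The complementary category reads: "Non-responder: namely the frequency of seizures remains or decreases but not up to 50% of the initial seizure frequency", and also takes in any increase. An unchanged frequency is therefore a non-response. Nothing is said about a baseline of zero.

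Eligibility does not bound the count. Besides age, entry rests on the diagnosis ("Children diagnosed as drug-resistant epilepsy by pediatric neurologists, diagnosis was based on the ILAE 2017 criteria") and on prior treatment ("Children will have got at least 3 months of combination therapy that consists of levetiracetam of topiramate with optimal of therapeutic dosages"). The only exclusion tied to recent seizure history is an upper one: "Suffered from status epilepticus in the prior 3 months before the study begins".

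Under Data collection, Baseline data, the CRF records "seizure frequency or average number of seizures per month", with no period given over which to count or average. Study procedure has enrolled children "then start the 3-day baseline phase" and takes seizure frequency from the medical record. The Diary Card section limits diary entries to the intervention phase.

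Study procedure also carries a second rule: a child who completes all phases is a responder.

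**The concern.** A percentage change needs a denominator that is above zero and large enough to be stable. This plan guarantees neither. The Introduction describes drug resistance as failure to become seizure-free, which a child with one seizure a month satisfies.

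Two things follow under Outcome evaluation, item a. A child recorded at zero who stays at zero is a treatment failure, whatever the drug did. A child recorded at one is a responder whenever the follow-up month happens to be empty. The first lowers both responder percentages and the second raises both. Either way the gap between the arms narrows, and that gap is what the trial was sized to detect.

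**Working it through.** **1. The plan's sample size.** Inputs from Sample size: Zα = 1.96, Zβ = 0.84, P1 = 0.95, P2 = 0.70, P = 0.825, Q = 0.175, and Q1 as printed, 0.5.

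n = [(1.96√(2 × 0.825 × 0.175) + 0.84√(0.95 × 0.5 + 0.7 × 0.3)) / 0.25]² = 48.9, against a stated 49.56, rounded to 50 per arm.

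Since 1 − 0.95 is 0.05, the same formula with Q1 = 0.05 gives 35.0, or 36 per arm. So 50 per arm gives more than the planned 80% power. That slip is a separate matter, but it explains the high starting power in step 5.

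**2. Chance response, baseline equal to an unchanged true rate b.** Assume Poisson monthly counts and a one-month follow-up window. The chance of a response is P(X ≤ b/2) with X ~ Poisson(b).

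| b per month | threshold | chance response |
|---|---|---|
| 0 | none possible | 0% |
| 1 | X = 0 | e⁻¹ = 36.8% |
| 2 | X ≤ 1 | 3e⁻² = 40.6% |
| 4 | X ≤ 2 | 23.8% |
| 8 | X ≤ 4 | 10.0% |

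**3. Other models**, at true rates of 1, 1.5 and 2 a month, given a non-zero baseline:
- Poisson, one random baseline month: 53%, 44%, 37%.
- Poisson, baseline averaged over 3 months: 40%, 32%, 29%.
- Negative binomial with dispersion parameter 1, one random baseline month: 64%, 58%, 54%.

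The range is about 29% to 64%. The fall at higher counts depends on the Poisson assumption: the same negative binomial model still gives 46% at 4 a month and 41% at 8.

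**4. How often zero arises.** Under Poisson a seizure-free month has probability e⁻¹ = 37% at 1 a month and e⁻² = 13.5% at 2. The 3-day phase cannot stand in for a month: at 1 a month it is empty with probability e^(−0.1) = 90%.

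If a share z of children have a zero baseline and count as failures, both rates are multiplied by 1 − z. At an illustrative z = 10%, 95% and 70% become 85.5% and 63%, a gap of 22.5 points instead of 25.

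**5. Dilution by chance responders.** Assume that 70% and 95% are free of chance response and that 40% of true non-responders with low counts are misclassified. With a share f of low-count children, the observed rate is P + (1 − P) × 0.4 × f.

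| f | control | first-line | gap | exact power, 50 per arm |
|---|---|---|---|---|
| 0 | 0.70 | 0.95 | 25 points | 94.8% |
| 0.5 | 0.70 + 0.30 × 0.2 = 0.76 | 0.95 + 0.05 × 0.2 = 0.96 | 20 points | 87.8% |
| 1 | 0.70 + 0.30 × 0.4 = 0.82 | 0.95 + 0.05 × 0.4 = 0.97 | 15 points | 73.7% |

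Power is for the uncorrected two-sided chi-square test at 5%. In the last row the smaller expected cell is 50 × (0.18 + 0.03)/2 = 5.25, so the Fisher fallback in Statistical Analysis, item 1, would often apply. Fisher power is about 78% in the second row and 58% in the third.

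**The case against.** Four objections carry weight.

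**The planning rates may already contain chance responders.** Sample size presents 70% as a proportion found with standard drugs and cites a guideline. An observed proportion includes whatever chance response occurred. If so, 70% does not become 82%. This stands, and it makes the power figures conditional.

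**The 74% is an extreme case.** It needs essentially every child to have 1 or 2 seizures a month, and the documents give no baseline distribution. With half the children at such counts, chi-square power is 88%, above the planned 80%. A reader might infer that the trial is underpowered; the documents do not support that.

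**The windows are not defined.** The CRF allows an average, so one empty month need not mean a zero baseline, and the follow-up month is not named either. If a halving had to hold in each of three months, the Poisson model gives 0.368³ = 5% at 1 a month and 0.406³ = 7% at 2. This stands too, but it shows the gap: the error rate depends on a choice that the plan leaves open.

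**The completion rule points elsewhere.** A reader might infer that a zero-baseline child can never be a responder. That is true only under Outcome evaluation, item a. Under Study procedure the same child could complete all phases and count as one. The two passages conflict, which does not cure the problem.

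A reader might also infer a bias toward one arm. Nothing here supports that: the mechanism works alike in both randomised groups.

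**Conclusion.** The point holds in a limited form. Three parts are matters of text: eligibility has no minimum count, the baseline look-back is not stated, and under Outcome evaluation, item a, a zero baseline cannot yield a response. The 37% to 41% chance response at 1 to 2 a month rests on a Poisson model, an unchanged true rate and a single-month comparison.

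The consequence is dilution of the difference, of unknown size. The 88% and 74% are illustrations that assume planning rates free of chance response; neither is an estimate for this trial. A short amendment is worthwhile because it removes an avoidable source of noise from the primary endpoint, not because the trial has been shown to fail without it.

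**What to change.** 1. **Minimum count.** Add to the inclusion criteria a minimum baseline seizure count, at a level agreed before enrolment. It should be at least one, so that the endpoint is defined, and preferably higher. Under Poisson, 4 a month leaves 24% chance response and 8 leaves 10%.
2. **Look-back.** Count it over a stated period within the 3 months on combination therapy already required. A longer baseline alone is not enough: with a 3-month average and a one-month follow-up, chance response is still 40% at 1 a month and 29% at 2, and a zero over the period still needs a rule.
3. **Follow-up window.** Name the diary period compared with baseline, as long as the schedule allows, and express both as rates over the same unit of time.
4. **Supportive analysis.** Add a negative binomial model of diary counts by arm, adjusted for baseline rate. It uses the size of the change and does not turn on one seizure at a threshold.
5. **One definition.** Reconcile the responder rules in Study procedure and Outcome evaluation, item a, so that each child has one classification.

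Cost: some rarely seizing children become ineligible, which may slow recruitment. Baseline counts will rest on records, because diaries start only in the intervention phase. Otherwise it takes a short amendment and one extra analysis of data already collected.

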older agents. On the other hand, topiramate, levetiracetam, oxcarbazepine are newer agents that are taken frequently for the second-line AEDs. 12, 13 The American Academy of Neurology (AAN) subcommittee reports in 2004 observed that newer AEDs were not different in controlling seizures but have better tolerability, particularly fewer neurotoxic adverse effect.¹⁴-¹⁶ There have been many studies comparing the efficacy and safety between first and secondline AEDs in newly diagnosed epilepsy children, showed that first-line agents are as efficacious as second ones. Guerreiro reported that seizure freedom rate in childhood absence epilepsy treated with phenytoin did not differ from those with oxcarbazepine.¹⁷ A study in Turki explained valproic acid, carbamazepine and phenobarbital have the same efficacy as levetiracetam for newly diagnosed epilepsy children. 18 The results was in line with that was reported by James, that valproic acid, carbamazepine as first-line agents and topiramate as the second one are equally effective to treat newly diagnosed epilepsy children. 19 While for drugresistant epilepsy, previous research investigated that children did not get seizure-free although they have been treated with levetiracetam, known as second-line AED, as add-on therapy.²⁰ However, there is no robust evidence for therapeutic efficacy of first-line AEDs as substitution of second-line ones. When it comes guideline therapy, there has not been any international guideline of combination therapy for the management of drug resistant epilepsy, even though many recommendations that have been made regionally in certain countries.

In the local situation in Indonesia where the study will be conducted, there are some challenges in the management of drug-resistant epilepsy in children. Similar to those in other countries, a study at Cipto Mangunkusumo General Hospital, Jakarta, showed that around 43% and 31% did not get seizure remission children although they have been given topiramate or levetiracetam respectively. Besides, from the factual situation at outpatient pediatric neurology clinic in Jakarta, the capitol of Indonesia, the number of the drugs that were covered by social insurance are limited so that sometimes patients should buy themselves the uncovered drugs that are needed. Moreover, the newer agents are sometimes not available even in the referral hospitals in other cities spreading all over the country.

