Randomized studies in drug-resistant epilepsy typically involve addition of new anti-epileptic drugs. However, in clinical practice, if the patient is already taking multiple drugs, then substitution of one of the current medications commonly occurs, despite little evidence supporting this approach.²² The choice of the substitution drug depends on the mechanism of action, the pharmacokinetic profile, drug-drug interaction, and the risk of seizure exacerbation as well as patients-related factors. The new combination is intended to maximize efficacy and minimize toxicity. However, the availability and cost-effectiveness should also be

taken into consideration since the patient would not reach the goal of ideal combination of drugs if they could not afford it nor even get the medication. ²³⁻²⁶ Another considerable case is one of drug resistance patterns in which at the first-time patients may not responsive to treatment yet they change into a state that is responsive to the medication. ²⁷ The choice of substitution therapy may originate from firs-line AEDs since evidences have shown they have equal efficacy to those of second-line ones. However, there is still lack of evidence whether the drug resistance pattern occur if the substitution drug is originated from first-line AED even more if it has ever been given prior to the current drug combination. ²⁷ The study aims to analyzed the efficacy and safety of first-line AEDs as substitution therapy in drug-resistant epilepsy children.

Primary Objective

The primary outcome of the research is to analyze the proportion of responders, who are defined as subjects who get 50% of seizure reduction.

Secondary Objectives

There are some secondary objectives of the study. The first one is to analyze the differences of improvement of quality of life, EEG feature and time to achieve seizure reduction, between the intervention and the control group. Besides, the research will describe the clinical characteristics, adverse effects of the drugs and laboratory features related to the adverse effects, among children with drug-resistant epilepsy. Furthermore, it will explain factors influencing the reduction of seizure frequency

Study Design

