EEG recording results are categorized into:

- Normal: does not show of hypofunction/asymmetry/epileptiform waves
- Abnormal: shows a picture of hypofunction/asymmetry/epileptiform waves or a combination of 1 or more of these features

The subjects who show changes in their EEG are later grouped into groups of abnormal to normal or abnormalities that showed improvement. Abnormalities that show improvement, for example are hypofunction (slowing down) waves experience improvement or decreasing number of epileptiform waves.

Next, a proportion calculation is carried out in the form of the percentage to subjects who experience a change in the EEG and will be categorized into:

- Different : when a significant difference is shown in difference of proportion test of the group that reuses first line OAE line as substitution therapy and those that use standard therapy/
- Not different: when there is no significant difference is shown in difference of proportion test of the 2 groups.
- d. Difference in actual failure between the groups reusing first line OAE as substitution therapy and those taking standard therapy. Description of drug side effects in the form of frequency distribution and percentage of side effects in each group. Description of laboratory results in the form of frequency distribution and percentage of side effects in each group
- e. Factors contributing to decrease in seizure frequency (age, seizure onset, seizure type, family history of seizures, developmental delay, history of OAE, initial seizure frequency, initial EEG, structural brain abnormalities)

Sample size

The estimated sample size in this study was calculated using the different proportion formula for the 2 unpaired groups as follows ²⁹:

$$n1 = n2 = (\frac{Z_{\alpha}\sqrt{2PQ} + Z_{\beta}\sqrt{P1Q1 + P2Q2}}{P1 - P2})^{2}$$

Description:

n1 number of subjects who received the new drug (First Line OAE)

n2 number of subjects receiving standard drug (Second line OAE)

Alpha type one error (5%)

Zα alpha standard value 5% one-way hypothesis (1,96)

Beta type two error (20%)

Zβ beta default value 20% (0,84)

P2 proportion of decreased seizures on standard drugs (reference) for example 0.7

Q2
$$1-P2 = 1-0.7 = 0.3$$

P1-P2 difference in the proportion of reduced seizure that is considered significant between the new drug and the standard (defined by the researcher) for example 25% (0.25)

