P1 proportion of reduced seizure on the new drug (the proportion of reduced seizure on the standard drug in addition to the minimal difference that is considered significant)= 0.7 + 0.25 = 0.95

Q1
$$1 - P1 = 1 - 0.95 = 0.5$$

P
$$(P1 + P2) / 2 = (0.95 + 0.7) / 2 = 0.825$$

Q
$$1-P = 1-0.825 = 0.175$$

In this study, it was found that the proportion of seizure reduction on standard drugs was 70%.³⁰ Therefore the equation:

$$n1 = n2 = \left(\frac{1,96\sqrt{2(0,825)(0,175)} + 0,84\sqrt{(0,95)(0,5) + (0,7)(0,3)}}{0,25}\right)^2 = 49,56 = 50$$

$$n\ 2\ groups=100$$

Based on the formula above, 100 research subjects are required. An additional of 10% from the total number of subjects are needed as there is a possibility of those dropping out, therefore a total of 110 subjects are needed in this study.

Statistical Analysis

- 1. Analysis of differences in the proportion of responders (primary outcome), differences in EEG appearance (secondary outcome) in pediatric epilepsy patients who are resistant to the combination of second line OAE between those who reused first line OAE as substitution therapy and those who used standard therapy. Data type is categorical. Data is analyzed the Chi-square statistical test, if it does not meet the requirements then an alternative test is performed, known as Fisher's multiple test. The significance level (α) is 5% and the research confidence level is 80%. If p value ≤ α is obtained, this means H0 is rejected, which means that there is a difference seen in seizure frequency between reusing first line OAE as substitution therapy and standard therapy.
- 2. Analysis of differences in the mean quality of life with an unpaired T test if the data distribution is normal or Mann-Whitney if data distribution is not normal
- 3. To assess drug effectiveness, the analysis used was the difference in actual failure between those using first line OAE as substitution therapy and those using standard therapy (primary outcome). Formula:

$$ARR = CER - EER$$

CER: the incidence of increased seizure frequency in the standard therapy group ERR: the incidence of increased seizure frequency in the group in substitution therapy with 1st line OAE The increase in seizure frequency in this study shows therapy

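### Any non-significant test on responders or EEG is recorded as *Not different*, with no confidence interval or margin to support that verdict

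*Combined protocol and SAP*

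**What the plan says.** Outcome evaluation, item a (responders, the primary outcome) says that "the percentage of respondents in the two groups is calculated and differentiated, therefore it is classified into two groups": *Different* if the two-group proportion test is significant, and otherwise "Not different: when there is no significant difference is shown in difference of proportion test of the 2 unpaired groups". Item c (EEG change) repeats the rule: "Not different: when there is no significant difference is shown in difference of proportion test of the 2 groups".

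Statistical Analysis, item 1, gives the test for both outcomes: chi-square, with a Fisher test as the fallback, rejecting when p is at most 5%. It adds "The significance level (α) is 5% and the research confidence level is 80" per cent. No interval is attached to that 80%. It equals one minus the 20% type II error in the Sample size section, so it appears to mean power.

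The Sample size section takes 70% response on standard drugs and sets the first-line rate as that figure "in addition to the minimal difference that is considered significant", which is 25 points.

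The Introduction points both ways. It says of first-line drugs that "evidences have shown they have equal efficacy to those of second-line ones", and also that "there is no robust evidence for therapeutic efficacy of first-line AEDs as substitution of second-line ones".

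**The concern.** The planned test asks whether the data are inconsistent with no difference. If it is non-significant, the difference may be small, or the trial may simply be too imprecise to say. Only an interval, or a margin with a trial sized for it, can tell these apart, and the plan has neither.

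Three items come close but do not fill the gap:

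- The 25 points is a superiority difference used for sample size. It is not a margin.
- The absolute risk reduction in Statistical Analysis, item 3, is a bare formula on a different event, increased seizure frequency.
- The difference in responder percentages is planned, but without any measure of its precision.

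The rationale for the trial rests partly on equal efficacy and on the cost and availability of the newer drugs. A recorded verdict of *Not different* could easily be read as support for substituting first-line drugs, even when a large loss of response has not been excluded.

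**Working it through.** **Inputs.** From the plan: 50 per arm (55 if all 110 are recruited and analysed), control response 70%, planned gain 25 points, alpha 5%. Assumed: the chi-square is uncorrected and two-sided. The plan does not mention a continuity correction. It calls the hypothesis one-way but uses 1.96, which is the two-sided value.

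**The plan's own sample size.** With its printed inputs, including Q1 = 0.5:

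[(1.96 × √(2 × 0.825 × 0.175) + 0.84 × √(0.95 × 0.5 + 0.7 × 0.3)) / 0.25]² = [(1.053 + 0.695) / 0.25]² = 48.9

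The plan states 49.56, rounded to 50. (1 − 0.95 is 0.05, not 0.5, and the corrected value gives 36 per arm. That is a separate matter, and 50 per arm is kept below.)

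**Which results receive the label.** Fix control at 35/50. For x first-line responders, z = ((x − 35)/50) / √(p(1 − p) × 2/50), with p = (x + 35)/100.

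- x = 26: p = 0.61, z = −0.18/0.0976 = −1.85, p value 0.065.
- x = 43: p = 0.78, z = 0.16/0.0828 = 1.93, p value 0.053.
- x = 25 and x = 44 give p values of 0.041 and 0.027, both significant.

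So 18 results, 26/50 to 43/50 (52% to 86%), are all *Not different*.

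**What those results leave open.** The 95% score interval (Mee) contains every difference δ for which |d − δ| / √(p̃₁(1 − p̃₁)/50 + p̃₂(1 − p̃₂)/50) ≤ 1.96. Here d is the observed difference, and p̃₁ and p̃₂ are the maximum-likelihood rates constrained to differ by δ.

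| First-line, against 35/50 | 95% CI (points) |
|---|---|
| 26 | −35.9 to +1.1 |
| 33 | −22.0 to +14.2 |
| 34 | −19.9 to +16.0 |
| 35 | −17.9 to +17.9 |
| 36 | −15.8 to +19.7 |
| 38 | −11.5 to +23.2 |
| 40 | −7.1 to +26.7 |
| 43 | −0.2 to +32.0 |

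None of the 18 intervals lies within ±15 points, and only three (34, 35, 36) lie within ±20. Eight (26 to 33) do not exclude a 20-point loss. Four (40 to 43) do not exclude the planned 25-point gain.

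**How often the label appears when first-line drugs are worse.** Exact binomial enumeration, control rate 70%:

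| True difference | 50 per arm | 55 per arm |
|---|---|---|
| −10 points | 82% | 80% |
| −15 points | 66% | 62% |
| −20 points | 45% | 42% |
| +25 points | 5% | 4% |

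For control rates from 40% to 80% at 50 per arm, the first three rows range over 79–82%, 61–66% and 40–46%. At +25 points, Fisher's test at 50 per arm gives 10%.

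**Why the interval level must be stated.** If the 80% were taken as the level, the score interval for 26 against 35 would be −29.9 to −5.5 points. That excludes zero although p = 0.065.

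The plan gives no expected rate of EEG change, so no figure is offered for item c.

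**The case against.** The best defence is that the label is defined in the plan as no significant difference being shown, so it is a coding term and not a claim of equality. The plan never says that a non-significant result establishes equivalence. The trial is sized to detect a gain, and a test of difference needs no equivalence margin. The rates of 82%, 66% and 45% are ordinary type II errors at losses the trial was not designed to detect, and new wording will not change them. At the plan's own alternative the miss rate is about 5%, well inside the allowed 20%. Since both percentages will be reported, a reader could work out the interval.

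Much of this stands. The harm is a risk of misreading, the lack of a margin is not in itself a fault, and the type II errors show only how weak a basis the label has. The counts also depend on the assumptions: with Yates' correction 25/50 also receives the label, and the upper limit at 39/50 is 24.99 points, so another interval method could make the count of four into five.

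The defence does not justify the rule itself. The two-way classification is the stated conclusion for the primary outcome, it has no place for an inconclusive result, and no interval is planned that would correct the impression it gives.

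**Conclusion.** The concern holds. For responders and EEG, the plan turns every non-significant result into a verdict that such a result cannot support. Against 35/50 on control, the verdict covers first-line results from 52% to 86%, and even identical observed rates leave about 18 points open in either direction. These figures assume 50 per arm, an uncorrected two-sided 5% chi-square test and the plan's 70% control rate.

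This is a fault in the stated conclusion and its reporting. The test remains valid, and the change should be made because it is cheap and affects how the primary result will be read.

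The quality-of-life label, "Not different, if there is no difference in the average quality of life", is not tied to a significance test, so it falls outside the main point.

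**What to change.** - For items a and c, report the difference in proportions with a 95% confidence interval. Inverting the score test (Mee, or Miettinen-Nurminen without the variance correction) keeps the interval in agreement with the uncorrected chi-square. Across the 2,401 tables with 1 to 49 responders per arm of 50, it never disagrees, whereas Newcombe disagrees in 8 and Wald in 12. Any stated 95% method would meet the main need. If Fisher's test is used, take significance from its p value.
- State the level as 95%, and correct the 80% confidence level if power is meant.
- Replace *Not different* with *no significant difference shown*. For each such result, give the largest loss and largest gain the interval does not exclude and, for responders, say whether the 25-point gain is excluded. This would separate 26/50 (loss of up to 35.9 points not excluded) from 38/50 (up to 11.5 points).
- State that non-significance will not be described as equal efficacy, because no margin was set.
- For consistency, replace the label in item b with the mean difference and 95% interval, or the Hodges-Lehmann shift if Mann-Whitney is used.

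The cost is wording and an interval calculation, with no change to the test, data collection or sample size. The downside is that many null results will read as inconclusive and could not be presented as equality.
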